5.4. Washout period

Following the endpoint assessment, subjects will enter a 1-week \pm 3 day washout period during which they will not receive any study medications.

At 3 weeks into each interventional phase, the Actigraph device will be mailed to the subjects. The goal will be for the subjects to wear this devices on their wrist during the final week of each interventional phase to look for differences with each therapy. The device will be returned by the subject at the endpoint assessment.

5.5. Intervention Phase 2

Following the washout period, subjects will receive either active drug (KNO₃) or control (KCI) during phase 2 of the trial. Subjects will receive the intervention (KNO₃ or KCI) that was not administered to them in phase 1, such that each subject will receive both study interventions in this cross-over design. The ~1-week call and the ~4-week study visit will be repeated as above. We will provide subjects with a 14-day supply of study medication to account for potential delays in receipt of the 2nd batch of medication (i.e., after the 1-week call).

1-week call: Subjects will be called by telephone ~1 week later to assess if they are experiencingside-effects. Subjects will receive reinforcement of the dietary restrictions imposed during the study. Subjects will be asked about headaches and dizziness. If these symptoms are not present, or are not different than the subject's baseline, the drug dose will be up-titrated to 18 mmol daily (One 6-mmol capsule taken 3 times per day). The presence of orthostatic symptoms will prompt a visit to assess for orthostatic vital signs. The presence of symptomatic orthostatic hypotension (20 mmHg reduction in systolic blood pressure with associated symptoms such as dizziness) at the follow up visit will prompt exclusion of patients from the trial.

Phase 2 endpoint assessment: Following 4 ± 1-weeks of therapy with KNO₃ or KCl, subjects will return for a repeat endpoint assessment. Physical examination with measurement of orthostatic blood pressure, KCCQ, dietary counseling, and side effect assessments will be performed. A urine pregnancy test will be performed in women with childbearing potential. An intravenous catheter will be placed in the antecubital vein and securely fixed in place. Blood, urine and saliva samples will be collected prior to, and approximately 2 hours after, morning dose administration, given with a standardized low-nitrate breakfast. Blood RNA samples will be collected prior to the morning dose administration using Paxgene tubes (BD Biosciences, Franklin Lakes. NJ). Subjects will then undergo repeat echocardiography, arterial tonometry and blood pressure measurements (including BP+ central blood pressure measurements). Subjects will then perform a maximal-effort peak oxygen consumption (VO₂) test using a supine bicycle exercise test with expired gas analysis. Cardiac output at rest will be measured immediately prior to exercise using pulsed wave Doppler echocardiography. An additional blood sample will be obtained at peak exercise. Flow-mediated dilation of the brachial artery to assess endothelial function will be performed (Unex Co. Ltd., Nagoya, Japan). The Kansas City Cardiomyopathy Questionnaire (KCCQ) will be administered. Download of actigraph device data will also be done.

Following the final endpoint assessment, subjects' participation in the study will be over.

Phase 2 visit (final visit)

- Interim medical history, review of concomitant medications
- Physical Exam (including orthostatic vital signs)
- Blood, urine, saliva collection
- Blinded drug administration
- ECG, laboratory tests (CBC, comprehensive metabolic panel, methemoglobin; pregnancy test as needed, BD PAXgene RNA samples
- KCCQ
- Blood, urine and saliva collection approximately 2 hours post-administration
- Echocardiogram, arterial tonometry
- Cardiopulmonary test with resting cardiac output measurements, blood draw at peak exercise
- Download of Actigraph data and continuation of outpatient physical activity
- Endothelial function assessment with flow-mediated brachial artery dilation

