5.2. Randomization procedure

A blocked randomization will be performed. Each block will contain an equal number of allocations to KNO₃ followed by KCI versus KCI followed by KNO₃. The order of treatment sequences within each block will be randomized.

5.3. Intervention Phase 1

Subjects will be randomized to receive either active drug (KNO₃) or control (KCI) as the "first" drug for phase A. The initial dose will be one 6 mmol capsule administered twice daily, to be taken with meals. We will provide subjects with a 14-day supply of study medication to account for potential delays in receiving the 2nd batch of medication (i.e., after the 1-week call).

1-week call: Subjects will be called by telephone ~1 week later to assess if they are experiencing any side-effects. Subjects will receive reinforcement of the dietary restrictions imposed during the study. Subjects will be interrogated about headaches and dizziness. If these symptoms are not present, or are not worse compared to the subject's baseline, the drug dose will be up titrated to 18 mmol daily (One 6-mmol capsule taken 3 times per day). The presence of orthostatic symptoms (i.e. sustained lightheadedness upon standing) will prompt a visit to assess for orthostatic vital signs. The presence of symptomatic orthostatic hypotension (20 mmHg reduction in systolic blood pressure with associated symptoms such as dizziness) measured at this subsequent assessment visit will prompt exclusion of patients from the trial.

For subjects who have a serum K at the initial visit between 4.7 and 5.0 mEq/L in the presence of either: (a) potassium-sparing diuretic use, or (b) Estimated glomerular filtration rate of 30-39 mL/min/1.73m2, we will check a serum potassium 1 week after the implementation of the 18 mmol/d dose as a safety measure. A serum potassium > 5.5 mEq/L will prompt exclusion at this point.

At 3 weeks into each interventional phase, the Actigraph devices will be mailed to the subjects. The goal will be for the subjects to wear this device on their wrist during the final week of each interventional phase to look for differences with each therapy. The devices will be brought back by the subject at the endpoint visit.

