5.6. Adverse Event Reporting

All adverse events and adverse device effects will be reported following FDA guidelines. The research team will keep a log of all adverse events that occur in the trial, and any reportable events will be reported as described in Section 7 of this protocol. The study team in charge of the conduct of the trial is up to date on all trainings pertaining to safety guidelines and adverse event reporting. Adverse Events will be reported to the site IRB, the Sponsor and the NIH Program Office in a timely fashion, as specified in section 7.

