6. DRUG DISPENSING, ACCOUNTABILITY AND DESTRUCTION

 KNO_3 and KCI capsules will be prepared at the University of Pennsylvania Investigational Drug Service [[name]]. Drug bottling, labeling and dispensing will also be managed by the Penn Investigational Drug Pharmacy. Prior to initiation of each phase, participants will receive a sufficient supply of KNO3 or control capsules to last until the end of each treatment phase, allowing for 100% compliance with the regimen for the entire treatment phase, including a window of ± 7 days for the 1-week uptitration (to ensure an adequate supply of medication before additional medications are received by the subject) and ± 1 week for the endpoint assessment visit.

Subjects will be instructed to take the medication as required by the protocol, and compliance will be assessed via pill count performed by IDS.

Subjects will be instructed to return unused capsules at the end of each treatment phase. A pill count will be performed by IDS prior to destruction of the drug. Returned trial capsules will be stored separately from the non-allocated trial capsules until returned trial capsules are disposed of. The IDS personnel will keep track of all received, used, partly used and unused trial products.

Used and unused study drug will be destroyed at the instruction of the sponsor. A copy of the drug destruction SOP should be maintained in the pharmacy section of the Regulatory Binder. Study drug should not be destroyed until drug accountability has been completed.

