7.3. Recording and Reporting of Adverse Events

The site PI will continuously supervise all aspects of the trial and review the records of the study

subjects following each visit and at the end of their participation. The site PI will be responsible for ensuring that all adverse events are noted, followed and reported to the IRB, Sponsor (at [contact]) and IND Medical Director as appropriate.

SAEs occurring from the time of signed informed consent to the final study visit will be captured on the SAE eCRF. AEs will be classified according to the guidelines/definitions specified in section 7 of the protocol. Any AE rated \geq 3 in severity (i.e., SAE) must be reported by the site investigator or qualified designee within 1 working day of first becoming aware of the event, to the sponsor via email and regulatory medical director. The IRB should be notified as per institutional guidelines. The medical director and site IRB, as appropriate, will make an immediate determination about the necessity to modify the protocol, include additional information in the consent form, inform previous participants, temporarily hold enrollment of patients, or terminate the study. The study will proceed only if the medical director and site IRB all agree on this course of action.

The investigator or qualified designee will enter the required information regarding the SAE into the appropriate module of the eCRF, All study procedures and cumulative adverse events are subject to full IRB review at least yearly.

Events significant enough to necessitate modification of study drug dosing will be captured on an appropriate eCRF module ("Study Drug Dosing" page). Should the PI determine that modification to the study drug is appropriate, the PI must notify the sponsor.

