7.5. Management of Suspected Unexpected Serious Adverse Reaction

AEs that meet the criteria of serious, related to study intervention, and unexpected for the study intervention, qualify for expedited reporting by the sponsor to the regulatory authorities. The Site Investigator will assess all SAEs and evaluate for "unexpectedness" and relationship to study drug. The Site Investigator is required to complete a report for any events identified as serious, study drug related and unexpected, using the CIOMS format. The sponsor will submit a voluntary CIOMS form. See Section 7.4 for reporting procedures.

A copy of this report should be kept at the site and also forwarded to the sponsor regulatory lead within the same timeline used for reporting to regulatory authorities.

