
8.5. Blood nitrate/nitrite level measurements

We will document an intervention-related change in blood nitrate and nitrite. Nitrate and nitrite

levels will be sampled before and approximately 2 hours after the last oral dose on the morning of the exercise test, after the patient has been on each intervention for 4 ± 1 weeks. Measurements will be performed at [name] lab at the University of Pennsylvania. Venous blood samples will be drawn into lithium-heparin tubes (which have very low levels of nitrate/nitrite) and centrifuged at 4,000 rpm for 10 min within 3 min of collection and frozen at -80°C for later analysis. Blood will also be obtained at peak exercise. After thawing at room temperature, blood samples will be deproteinized using cold ethanol precipitation as previously described.⁽⁹⁸⁾ The nitrate and nitrite content of deproteinized blood will be determined using a modified detection chemiluminescence technique using a lonics/Sievers nitric oxide analyzer (NOA 280), as first described by [name] lab⁽⁹⁹⁾ and later adapted by Allen et al for human blood.⁽¹⁰⁰⁾

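### Participation and the SAE capture window both close at the phase 2 visit, the day of the last dose and the second maximal exercise test, and the supplied text schedules no safety contact afterwards

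*Combined protocol and SAP*

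**What the plan says.** The phase 2 visit is labeled the final visit. Blinded study drug is given there, followed by a maximal supine bicycle test (section 5.5, Phase 2 endpoint assessment). Section 8.5 times the blood samples before and "approximately 2 hours after the last oral dose on the morning of the exercise test", which places the final dose on the same day. Section 6 has unused capsules returned at the end of each phase. After the visit, section 5.5 states: "Following the final endpoint assessment, subjects' participation in the study will be over".

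Section 7.3 sets the capture window: "SAEs occurring from the time of signed informed consent to the final study visit will be captured on the SAE eCRF". For non-serious events section 5.6 requires a log but gives no start or end date.

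Appendix 1 lists four adverse event assessments: at 1 week and at 4 ± 1 weeks in each phase. No column follows the last one.

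Three provisions deal with events outside the schedule. Reportable events are followed until they resolve, stabilize or are explained (7.4). Pregnancy is followed to its outcome (7.6). Subjects who withdraw are asked to attend a termination visit with an adverse event assessment (5.7). Section 13 refers to Appendix 3 for the data and safety monitoring plan, which is not in the supplied text.

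**The concern.** Testing the safety of KNO₃ is part of the trial's stated purpose (section 1). The subjects are aged 50 to 90 and have had an aortic valve replacement, and section 7.2 lists arrhythmia and unplanned hospitalization among the events expected in such patients. On the final day they take study drug, have a venous catheter placed and exercise to their limit. If something new begins that night or in the following days, nobody is scheduled to ask, and the SAE form's window has closed.

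The first treatment is handled differently. After phase 1 the subject stays in the study through the washout, the SAE window stays open, and section 5.5 provides that "The ~1-week call and the ~4-week study visit will be repeated as above", so someone asks about side effects again. The supplied text gives no reason for the difference. What is at stake is the completeness of the safety record after the second treatment.

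**Working it through.** The plan states no figure on this point, so the check is to set the relevant dates side by side and count who is affected.

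**1. What ends when**

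| Item | Source | Ends at |
|---|---|---|
| Study drug | 5.5, 8.5 | Morning of the phase 2 visit |
| Maximal exercise test | 5.5 | Phase 2 visit |
| SAE capture on the eCRF | 7.3 | Final study visit, which is the phase 2 visit |
| Scheduled adverse event assessment | Appendix 1 | Phase 2, 4 ± 1 weeks |
| Participation | 5.5 | After the phase 2 visit |

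All five end on one day. The number of scheduled contacts after that day is 0.

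**2. Whether another provision would find a new event**

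- 7.4 and 7.6 apply once an event or pregnancy is known. They do not detect new ones.
- 5.7 applies to subjects who withdraw, not to completers.
- 5.6 and 7.5 govern reporting and carry no end date, but they schedule no contact and do not extend the eCRF window.
- 7.3 has the site PI review each subject's records at the end of participation. That covers what has been recorded up to then.

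None is a scheduled contact that would bring a later event to light.

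**3. How many subjects**

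- Randomized: 22 (10.1). Retention: 90% (10.1).
- Completers: 0.9 × 22 = 19.8, about 20.
- Allocation is balanced within blocks (5.2: "Each block will contain an equal number of allocations to" each sequence), so 19.8 / 2 = 9.9, about 10 completers finish on KNO₃ and about 10 on KCl. This assumes similar retention in the two sequences.

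**4. How many events might be missed**

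This cannot be computed from the documents. They give no rate for events that begin after the final visit, and they name no delayed harm on stopping KNO₃. The procedure rates in 11.2.2 (hematoma in 2-3% and fainting in 1% at blood donation) do not describe that period. No expected count is derived.

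**5. Effect of the proposed call on timing**

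The washout in 5.4 is 7 ± 3 days, so a call on the same timing falls 7 − 3 = 4 to 7 + 3 = 10 days after the last dose.

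**The case against.** The strongest case against raising this has four parts.

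*Subjects are observed after the last dose.* The dose is given at the visit. Samples follow about 2 hours later, then echocardiography, tonometry, blood pressure, monitored exercise and brachial dilation. Exercise takes place in hospital with ECG, blood pressure and oximetry monitoring and a code team available (11.2.2, 11.3.2). The two main nitrate risks named in 11.2.1 are blood pressure and methemoglobin. Both are measured at that visit, and methemoglobin is said to reconvert at about 15% per hour. This stands. It lowers the likely yield, but it covers hours and not the following days.

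*Appendix 3 may already contain a closing contact.* This also stands. A reader might infer that the plan as a whole has no post-treatment follow-up. The supplied text cannot show that. It shows only that 5.5, 7.3 and Appendix 1 have none.

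*The three sections agree with each other, so this is a design choice.* That is true, and no contradiction is claimed. It is still a choice that can be improved at little cost.

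*The consequence is negligible.* It is probably small, but the documents do not allow a size to be given in either direction.

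Three stronger readings are tempting and are not supported:

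- *A late event would go unreported even if it became known.* Section 5.6 says "All adverse events and adverse device effects will be reported following FDA guidelines", and under 7.5 events that are serious, related and "unexpected for the study intervention, qualify for expedited reporting by the sponsor to the regulatory authorities". Neither has an end date. Likewise the 1-working-day rule in 7.3 runs from when the site becomes aware of the event.
- *The gap favors KNO₃.* With balanced sequences it falls about equally on both drugs.
- *The gap can be measured in days against phase 1.* Intervals after phase 1 do not measure what is absent after phase 2. The phrase "including a window of ± 7 days for the 1-week uptitration" in section 6 concerns drug supply, and the plan does not apply it to the timing of the call.

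**Conclusion.** The point holds as a minor one. In the supplied text nothing is scheduled to detect a new adverse event after the phase 2 visit, and the SAE eCRF window has closed by then. The result is possible under-capture, of unknown and probably small size, among about 20 completers. It does not bias the comparison between KNO₃ and KCl, and no efficacy endpoint, power figure or analysis changes.

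This rests on three assumptions: that the dose on the morning of the phase 2 exercise test is the final dose, as 8.5 and the capsule return in section 6 indicate; that retention is close to 90% and similar in the two sequences; and that Appendix 3 does not provide a closing contact. If the third fails, what remains is to bring 5.5, 7.3 and Appendix 1 into line with Appendix 3.

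**What to change.** - In 7.3, extend adverse event and SAE capture to about 1 week (± 3 days) after the last phase 2 dose, collected by one scripted telephone call. The length is taken from the plan's own washout in 5.4, not from a half-life.
- In Appendix 1, add the call as a final column with an adverse event assessment.
- In 5.5, end participation after the call.
- If Appendix 3 already specifies a closing contact, align 5.5, 7.3 and Appendix 1 with it instead.

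The cost is about 20 telephone calls of a kind the team already makes at 1 week in each phase, and wording changes in three places. The last subject leaves the study 4 to 10 days later. No additional visit or procedure is needed.

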5.6. Adverse Event Reporting

All adverse events and adverse device effects will be reported following FDA guidelines. The research team will keep a log of all adverse events that occur in the trial, and any reportable events will be reported as described in Section 7 of this protocol. The study team in charge of the conduct of the trial is up to date on all trainings pertaining to safety guidelines and adverse event reporting. Adverse Events will be reported to the site IRB, the Sponsor and the NIH Program Office in a timely fashion, as specified in section 7.

5.7. Subject withdrawal / Early termination

Subjects may voluntarily withdraw from the study at any time and for any reason, or this may be at the investigator's discretion. The investigator may withdraw a patient from the study due to protocol non-compliance, incorrect enrollment or randomization, or for any other reasons related to subject safety. The reason for study discontinuation will be recorded on the source documents and all such subjects will be asked to complete an early termination visit.

During this visit, we will document: (1) vital signs; (2) compliance with the medications (3) Adverse effects. (4) Specific reason for withdrawal.

Subject Early Termination Visit Procedures

- Vital Signs and Physical Exam
- Medication adherence log
- Safety Labs
- Adverse event assessment
- Documentation of reason for withdrawal

5.8. Concomitant Medication

Subjects should be treated with standard of care medications for AS or associated comorbidities. As per inclusion criteria, subjects should be on a stable medical regimen prior to entry. Further adjustment of blood pressure medications during the study period is discouraged and should only be performed according to new and clinically compelling worsening of clinical status. Therapy with organic nitrates or phosphodiesterase-5 inhibitors is contraindicated during the study period.

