Prior data demonstrates that a single oral dose of inorganic nitrate reduces late systolic load in other populations. Dietary nitrate increases plasma nitrite, an endothelium-independent source of the potent vasodilator nitric oxide (NO). Thus, augmentation of the nitrate-nitrite-NO pathway has the potential for chronic "disease-modifying" benefits in aortic stenosis. Therefore, nitrate supplementation represents a logical intervention to improve exercise capacity and quality of life in aortic stenosis.

The current trial is designed to assess the safety and efficacy of sustained oral administration of inorganic nitrate in patients with severe aortic stenosis and to assess the mechanisms by which inorganic nitrate enhances oxygen uptake and exercise capacity in this population. This is a randomized double-blind crossover clinical trial, in which 22 subjects who underwent surgical or transcatheter AVR for severe AS three or more months prior to enrollment will receive the following 2 interventions, in randomized order: (1) Potassium nitrate (KNO₃), at a dose of 12-18 mmol/d by mouth for 4 ± 1 weeks, or; (2) Potassium chloride (KCI), at a dose of 12-18 mmol/d by mouth for 4 ± 1 weeks. A 1-week ± 3 day washout period will be introduced between the 2 interventions. The purpose of the trial is to test the safety of KNO₃ and its efficacy on a number of clinical and physiologic endpoints in subjects who underwent AVR for severe AS.

Our specific aims are:

Specific Aim 1: To assess whether KNO_3 therapy improves endpoints with direct clinical relevance: aerobic capacity and quality of life (QOL)

Hypothesis 1a: KNO_3 will improve exercise capacity, quantified as: (1) Total work performed during a maximal-effort exercise test; (2) Peak oxygen consumption (VO₂) during a symptom-limited maximal effort exercise test. These will be the co-primary endpoints of the trial.

Hypothesis 1b: KNO_3 will improve QOL, assessed using the Kansas City Cardiomyopathy Questionnaire.

Specific Aim 2: To dissect the effects of KNO₃ on specific physiologic adaptations to exercise

Hypothesis 2a: KNO_3 improves the systemic vasodilator response to exercise, measured as the change in systemic vascular resistance during a symptom-limited maximal effort exercise test.

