4.3.1. Inclusion Criteria

- 1. Adults aged 50-90 years of age
- 2. Diagnosis of severe aortic stenosis prior to aortic valve repair
- 3. Successful trancatheter aortic valve repair via transfemoral procedural approach or successful surgical aortic valve repair at least three months prior to enrollment

4. Stable medical therapy: no addition/removal/changes in antihypertensive medications, or beta-blockers in the preceding 30 days.

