5.1. Initial Visit

During the baseline study visit, inclusion and exclusion criteria will be reviewed to ensure subject suitability. After eligibility has been confirmed, written informed consent will be obtained from the subject using Institutional Review Board (IRB)-approved documents. Informed consent will be

obtained before any study procedures. Subjects will be given the opportunity to have all questions regarding their participation answered in detail in a private setting before entering the study.

Following informed consent, a physical examination, with measurement of orthostatic blood pressures, will be performed. A urine pregnancy test will be performed in women with childbearing potential. Blood will be collected for measurement of (a) comprehensive metabolic panel; (b) complete blood count; (d) methemoglobin. A pregnancy test (for women of childbearing potential) and Glucose-6-phosphate dehydrogenase (G6PD) deficiency screening (for males of males of African, Asian or Mediterranean decent) will be performed as needed. Blood, urine, and saliva samples will be collected and frozen for nitrate/nitrite and biomarker level determination. The Kansas City Cardiomyopathy Questionnaire (KCCQ) will be administered. Subjects will also be given an informational brochure regarding foods that are high in nitrate/nitrite and thus should be avoided during the study.

Echocardiography will then be performed using a standardized protocol. Images will be obtained from the parasternal long axis, short axis, apical 5-, 4-, 3-, and 2-chamber, subcostal, and suprasternal views for offline analysis of myocardial strain. Dedicated ventricular chamber images will be obtained in the 4- and 2-chamber apical positions for determination of left ventricular volumes. Mitral inflow velocities, including color M-mode interrogation, will be assessed in the 4- chamber view. Tissue Doppler imaging will be performed at the mitral septal position, approximately 1-cm apical to the mitral valve plane. Additional images will be obtained in the parasternal short axis at the level of the papillary muscles, 2-chamber, and 4 chamber apical views for assessment of myocardial strain. Pulse-wave Doppler interrogation of the left ventricular outflow tract (LVOT) will be performed in the apical 5-chamber view.

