Impact of NO₃⁻ on methemoglobin levels: Nitrate supplementation increases serum nitrite levels through the actions of an enterosalivary circuit and reduction of nitrate to nitrite by anaerobic bacteria in the oral cavity.^(20,25-28) Methemoglobin is generated by the reaction of nitrite with hemoglobin. According to Toxnet, doses between 2-9 grams of NO_3^{-} have been associated with methemoglobinemia. The dose we will use in our study (18 mmol KNO₃) will provide only 1.11 grams (18 mmol $NO_3^- x$ 62 grams/mol $NO_3^- x$ 1mol/1000 mmol), which is well below this threshold. Moreover, this level of nitrate supplementation provides less inorganic nitrate than that found in a traditional Japanese diet, which is rich in vegetables (traditional Japanese diet provides 18.8 mg/kg of nitrate per day x 70 kg individual = 1.3 grams of nitrate).⁽¹²⁸⁾ Moreover, not a single cases of methemoglobinemia was observed in our pharmacokinetics trial, at the same doses used in this trial and in the same patient population. In the pharmacokinetics study we measured methemoglobin every half hour after the first administration as well as during steady-state continued oral administration at doses of both 12 mmol/d and 18 mmol/d and did not find any clinically-significant elevations in methemoglobin. We don't anticipate any significant issues with methemoglobinemia in this study since this is a problem that has been reported with nitrite, but not with nitrate at the doses used in this study.

Safety data:

In a double-blind randomized controlled trial in HFPEF, in which 12.9 mmol of inorganic were administered to patients with HFpEF, efficacy was demonstrated for the study endpoint (please refer to research plan). In this pilot study, no side effects were noted in any subject, except for pink urine (which was not different between the nitrate-rich and nitrate-poor beetroot juice,

because this is a consequence of other components of beetroot juice). As the body is able to reduce oxidized Fe³⁺ in methemoglobin back to Fe²⁺ at a rate of approximately 15% per hour,⁽¹²⁹⁾ the gradual increase in nitrite that occurs after nitrate administration (and the consequent formation of methemoglobin), should occur slowly enough to prevent significant rises in methemoglobin. To the best of our knowledge, methemoglobinemia has not been reported with oral nitrate administration. In our pharmacokinetic study, we did not observe any clinically-relevant elevations in methemoglobin levels⁽¹²⁷⁾.

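### The plan names oral bacteria as its route from nitrate to nitrite but neither restricts nor asks about antibacterial mouthwash, so the KNO3 contrast may be diluted

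*Combined protocol and SAP*

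**What the plan says.** On mechanism, section 11.2.1 explains the rise in serum nitrite after nitrate by an enterosalivary route and "reduction of nitrate to nitrite by anaerobic bacteria in the oral cavity". Section 1 identifies plasma nitrite as the source of nitric oxide, on which the expected benefit rests.

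On influences that could disturb the contrast, the plan acts in four places:

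- **Diet, section 5.1:** "Subjects will also be given an informational brochure regarding foods that are high in nitrate/nitrite and thus should be avoided during the study".
- **Diet, 1-week calls (sections 5.3 and 5.5):** "Subjects will receive reinforcement of the dietary restrictions imposed during the study".
- **Drugs, section 5.8:** "Therapy with organic nitrates or phosphodiesterase-5 inhibitors is contraindicated during the study period". Sections 4.3.2 and 11.3.3 carry matching exclusions.
- **Stability at entry, section 4.3.1:** "Stable medical therapy: no addition/removal/changes in antihypertensive medications, or beta-blockers in the preceding 30 days".

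Otherwise section 5.8 leaves background treatment open: "Subjects should be treated with standard of care medications for AS or associated comorbidities". Antibacterial mouthwash and antibiotics are not mentioned in the eligibility criteria, the visit instructions, section 5.8, section 10.2 or Appendix 1.

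On detection, compliance is judged by pill count (section 6). Concomitant medications are reviewed at baseline and at the two endpoint visits; Appendix 1 does not schedule that review at either 1-week call. For nitrate and nitrite, section 8.5 states that "levels will be sampled before and approximately 2 hours after the last oral dose on the morning of the exercise test". The trial summary table lists, as an exploratory aim, relating the levels achieved to each subject's response.

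**The concern.** If bacteria in the mouth carry out the conversion, an agent that suppresses them can weaken the intervention without any missed dose. A subject who uses antibacterial mouthwash daily can take every KNO3 capsule, pass the pill count and still enter the paired comparison with reduced exposure to nitrite. The plan guards against extra nitrate or nitric oxide entering from food and drugs, but not against loss of the conversion step.

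The main consequence is attenuation. The KNO3-minus-KCl differences in peak VO2, KCCQ and wave reflections would move toward zero, and subjects would differ more in their response. With about 20 completers, two affected people are 10% of the sample. Suppression confined to the KCl phase could act the other way by lowering nitrite formed from residual dietary nitrate, but the diet restriction makes this secondary.

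**Working it through.** **Inputs from section 10.1:** 22 enrolled; 90% retention, so 22 × 0.90 = 19.8, about 20 completers; two-sided α = 0.05; 80% power at effect size d = 0.66; SD of the change in peak VO2 1.23 ml/kg/min; minimum important change 0.6 ml/kg/min.

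**Input assumed:** f, the share of KNO3 phases that lose all conversion and hence all effect. The documents give no value, so 0 to 30% is shown.

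**Step 1: the plan's own figure.** Paired t-test, n = 20, 19 degrees of freedom, noncentrality d√n = 0.66 × √20 = 2.95. The noncentral t distribution gives power 79.9%, or 79.7% with 18 degrees of freedom. The stated 80% reproduces, and no figure in the plan is in dispute.

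**Step 2: dilution.** The mean standardised effect becomes d(1 − f). If the affected phases also add spread, the SD is multiplied by √(1 + f(1 − f)d²). For f = 10%:

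- diluted effect: 0.66 × 0.90 = 0.594
- SD factor: √(1 + 0.10 × 0.90 × 0.66²) = √1.0392 = 1.019
- effect with added spread: 0.594 / 1.019 = 0.583

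| f (assumed) | Diluted effect | Power, SD unchanged | Power, SD inflated |
|---|---|---|---|
| 0 | 0.660 | 79.9% | 79.9% |
| 5% | 0.627 | 75.8% | 75.0% |
| 10% | 0.594 | 71.2% | 69.6% |
| 20% | 0.528 | 61.1% | 58.2% |
| 30% | 0.462 | 50.1% | 46.7% |

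**Step 3: the plan's minimum important change.** Here d = 0.6 / 1.23 = 0.49. With the SD unchanged, power is 54.4% at f = 0, 46.2% at 10% and 38.1% at 20%.

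**Step 4: partial loss.** If affected phases lose only a share a of the effect, the mean becomes d(1 − f·a). For example, f = 20% with half the effect lost gives 0.66 × (1 − 0.20 × 0.5) = 0.594, the same diluted effect as the 10% row. The table is therefore the upper end for each f.

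**Step 5: do existing procedures close the gap?**

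- The pill count measures capsules taken, not conversion.
- The medication review should pick up prescribed antibiotics at endpoint visits, but nothing prompts for mouthwash.
- The nitrite assays can show a poorly converted phase. They do so when the endpoint is being measured, too late to prevent it, and without an exposure record they cannot say why nitrite was low.
- Section 10.2 has no rule that brings nitrite level or antibacterial exposure into any analysis of the co-primary outcomes.

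**The case against.** The strongest reply is that the trial already measures what matters. Nitrate and nitrite are assayed before and after the dose at each endpoint visit, blood is also drawn at peak exercise, saliva is collected, and concomitant medications are reviewed. Failed conversion would show as low nitrite. This stands, and it limits the concern to prevention, explanation and the absence of any preplanned use of the levels.

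Several stronger readings are tempting, but the documents do not support them:

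- **That nitrate works only through oral bacteria.** Section 11.2.1 gives this route without calling it exclusive, and mentions conversion to nitrite in the stomach when discussing a cancer concern.
- **That some KNO3 phases would be inactive.** The documents do not say how far, or for how long, mouthwash or antibiotics lower nitrite. Attenuation is as far as the inference goes.
- **That a null result could not be interpreted.** With nitrite measured in both phases, poor conversion can be distinguished from lack of effect despite adequate nitrite.
- **That the level-response aim would be confounded.** Low conversion appears as low nitrite, the very exposure that aim studies. Confounding would need a separate path from antibacterial use to outcome, and the documents give none.
- **That antibiotic courses will be common.** Section 7.2 lists endocarditis and sternal infection as expected events after AVR, but subjects are at least three months past the procedure, and the list gives no frequency.

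It is also fair to object that f has no source, that assigning affected phases no effect is extreme, and that the pilot SD may already contain some variation in conversion. The table is an illustration, not an estimate. The brochure itself is not in the documents; it is described as covering foods, so its silence on mouthwash is likely but unverified.

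**Conclusion.** The gap is real but modest. The plan names oral bacteria as its route from nitrate to nitrite, controls diet and two drug classes, and neither restricts nor specifically asks about antibacterial mouthwash. Attenuated conversion in some KNO3 phases is therefore possible and would mainly pull the within-subject differences toward zero.

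Its size is unknown. The range of about 70% power at f = 10% and 58–61% at f = 20% assumes complete loss in affected phases, effect size 0.66 and 20 completers; the true loss may be much smaller. Existing measurements can reveal an affected phase but cannot prevent it. The case for acting is that the stated power has no reserve at 20 completers and that prevention is cheap. This is a worthwhile improvement, not a fatal flaw, and the sample size calculation is not in error on this account.

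**What to change.** 1. In section 5.8 and the dietary brochure, ask subjects to avoid elective, non-prescribed antibacterial mouthwash from the start of phase 1 to the last endpoint visit, identically in both phases.
2. Add a prompt on mouthwash and antibiotic use to the 1-week calls and the endpoint visits, and record the answers.
3. Leave prescribed rinses and antibiotics entirely to clinical care and only record them. Do not move endpoint visits because of them, since that could make a subject's two phases unequal in length.
4. In section 10.2, add a sensitivity analysis of the co-primary outcomes that takes account of recorded exposure or the nitrite level achieved. Both arise after randomization, so this supports the main comparison and does not replace it.

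The cost is a few lines of text, one more instruction for subjects, and a little more recording and analysis. No visit, test or subject is added, and because the instruction is the same under KNO3 and KCl, blinding is unaffected. Some attenuation from prescribed agents may remain, but it would be on record.
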